7.7 Pharmacogenetic Studies

studied.

No additional blood will be collected for the pharmacogenetic analyses. If the subject consents to the optional pharmacogenetic portion of this study, deoxyribonucleic acid (DNA) analyses may be performed. These optional pharmacogenetic analyses focus on inherited genetic variations to evaluate their possible correlation to the disease and/or responsiveness to the therapies used in this study. The goals of the optional studies include the use of genetic markers to help in the investigation of cardiovascular disease, hyperlipidemia and other metabolic disorders and/or to identify subjects who may have positive or negative response to evolocumab.

7.8 Sample Storage and Destruction

Any blood sample collected according to the Schedule of Assessments (Table 3) can be analyzed for any of the tests outlined in the protocol and for any tests necessary to minimize risks to study subjects. This includes testing to ensure analytical methods produce reliable and valid data throughout the course of the study. This can also include, but is not limited to, investigation of unexpected results, incurred sample reanalysis, and analyses for method transfer and comparability.

All samples and associated results will be coded prior to being shipped from the site for analysis or storage. Samples will be tracked using a unique identifier that is assigned to the samples for the study. Results are stored in a secure database to ensure confidentiality.

If informed consent is provided by the subject, Amgen can do additional testing on remaining samples (ie, residual and back-up) to investigate and better understand the underlying inflammatory conditions, the dose response and/or prediction of response to evolocumab, and characterize aspects of the molecule (eg, mechanism of action/target, metabolites). Results from this analysis are to be documented and maintained, but are not necessarily reported as part of this study. Samples can be retained for up to 20 years.

Page 42 of 73

Since the evaluations are not expected to benefit the subject directly or to alter the treatment course, the results of pharmacogenetic, biomarker development, or other exploratory studies are not placed in the subject's medical record and are not to be made available to the subject, members of the family, the personal physician, or other third parties, except as specified in the informed consent.

The subject retains the right to request that the sample material be destroyed by contacting the investigator. Following the request from the subject, the investigator is to provide the sponsor with the required study and subject number so that any remaining blood samples and any other components from the cells can be located and destroyed. Samples will be destroyed once all protocol-defined procedures are completed. However, information collected from samples prior to the request for destruction, will be retained by Amgen.

The sponsor is the exclusive owner of any data, discoveries, or derivative materials from the sample materials and is responsible for the destruction of the sample(s) at the request of the subject through the investigator, at the end of the storage period, or as appropriate (eq. the scientific rationale for experimentation with a certain sample type no longer justifies keeping the sample). If a commercial product is developed from this research project, the sponsor owns the commercial product. The subject has no commercial rights to such product and has no commercial rights to the data, information, discoveries, or derivative materials gained or produced from the sample. See Section 11.3 for subject confidentiality.

8. WITHDRAWAL FROM TREATMENT, PROCEDURES, AND STUDY

8.1 **Subjects' Decision to Withdraw**

Subjects have the right to withdraw from the study at any time and for any reason without prejudice to their future medical care by the physician or at the institution.

Subjects (or a legally acceptable representative) can decline to continue receiving IP and/or other protocol-required therapies or procedures at any time during the study but continue participation in the study. If this occurs, the investigator is to discuss with the subject the appropriate processes for discontinuation from IP or other protocol-required therapies and must discuss with the subject the options for continuation of the Schedule of Assessments (Table 3) and collection of data, including endpoints and adverse events. The investigator must document the change to the Schedule of Assessments (Table 3) and the level of follow-up that is agreed to by the subject (eg, in person, by

Protocol Number: 20130286

Date: 30 January 2017

Page 44 of 73

telephone/mail, through family/friends, in correspondence/communication with other physicians, from review of the medical records).

Withdrawal of consent for a study means that the subject does not wish to receive further protocol-required therapies or procedures, and the subject does not wish to or is unable to continue further study participation. Subject data up to withdrawal of consent will be included in the analysis of the study, and where permitted, publicly available data can be included after withdrawal of consent. The investigator is to discuss with the subject appropriate procedures for withdrawal from the study.

8.2 Investigator or Sponsor Decision to Withdraw or Terminate Subjects' Participation Prior to Study Completion

The investigator and/or sponsor can decide to withdraw a subject(s) from IP and/or other protocol-required therapies, protocol procedures, or the study as a whole at any time prior to study completion.

Subjects may be eligible for continued treatment with Amgen IP and/or other protocol-required therapies by a separate protocol or as provided for by the local country's regulatory mechanism, based on parameters consistent with Section 12.1.

8.3 Reasons for Removal From Treatment or Study

8.3.1 Reasons for Removal From Treatment

Reasons for removal from protocol-required IP or procedural assessments include any of the following:

subject request

Product: Evolocumab

- subject request to end IP administration
- safety concern (eg, due to an adverse event, pregnancy in a female subject)
- death
- lost to follow-up
- administrative decision by Amgen (other than subject request, safety concern, or lost to follow-up)
- decision by the primary investigator/physician

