When IP is mandated to be administered at the study site, the date and completion time of administration, the body location of the injection, and whether the injection was administered fully, or partially, or not at all administered, in addition to the reason for a partial/lack of injection, are to be recorded on each subject's CRF provided. When IP can be administered at an appropriate non-clinic setting (eg, at the subject's home), a non-investigator site location, at a minimum, the dates that the devices were dispensed and the used devices were returned, the number of devices dispensed and returned, and number of devices administered fully, partially, or not at all, in addition to the reason for a partial/lack of injection, must be provided whether each device was returned fully or partially used are to be recorded on each subject's CRF.

Overdose with this product has not been reported.

6.2.1.3 **Open-label Period**

Product: Evolocumab

Subjects who receive a dose of IP at week 20 will continue in an open-label period. During the open-label period, all subjects will be treated with 420 mg evolocumab via AMD, or Al/pen. Dosing at week 24 is expected to be in-clinic while dosing for weeks 28, 32, 36, 40, 44, and 48 is expected to be in an appropriate non-clinic setting (eg, at the subject's home, even on weeks with in-clinic visits); however, subjects who do not wish to self-inject at home may return to the clinic for injection.

Protocol Number: 20130286

Date: 30 January 2017

Page 26 of 73

6.2.2 Dosage Adjustments, Delays, Rules for Withholding or Restarting,

No dose adjustments are allowed in this study. If, in the opinion of the investigator, a subject is unable to tolerate a specific dose of IP, that subject will discontinue IP but will continue to return for all other study procedures and measurements until the EOS visit.

If a dose of evolocumab is missed, administration should occur as soon as possible if there are > 7 days until the next scheduled dose. If there are less than 7 days before the next scheduled dose, the missed dose should be omitted and the next dose should be administered according to the original schedule.

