12.4 Investigator Responsibilities for Data Collection

The investigator is responsible for complying with the requirements for all assessments and data collection (including subjects not receiving protocol-required therapies) as stipulated in the protocol for each subject in the study. For subjects who withdraw prior to completion of all protocol-required visits and are unable or unwilling to continue the Schedule of Assessments (Table 3), the investigator can search publically available records [where permitted] to ascertain survival status. This ensures that the data set(s) produced as an outcome of the study is/are as comprehensive as possible.

Page 62 of 73

Protocol Number: 20130286 Page 63 of 73

Product: Evolocumab Date: 30 January 2017

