10.5.1 Analyses of Primary Efficacy Endpoint

10.5.1.1 Primary Analysis of Primary Endpoint

To assess the primary endpoint of the percent change from baseline in LDL-C at week 24, a repeated measures linear effects model will be used on the FAS to compare the efficacy of evolocumab with placebo. The repeated measures model will include terms for treatment group, stratification factors, scheduled visit and the interaction of treatment with scheduled visit. All LDL-C values observed will be used irrespective of whether a subject remained on IP, and missing values will not be imputed for primary analysis. If there are fewer than 5 subjects in one stratum, then the Hepatitis C status stratification factor will not be included in the repeated measures model. To account for the repeated LDL-C measurements within a subject across the visits, the repeated measures linear effects model will use an unstructured covariance.

Multiplicity adjustment procedures are defined in Section 10.1.

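### Protocol 8.3.1 lets the reasons for ending IP also end assessments, so off-IP week 24 LDL-C can be lost and the primary estimate overstated by an unknown amount

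*Protocol*

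**What the plan says.** **Removal.** Protocol 8.3.1 introduces its list with "Reasons for removal from protocol-required IP or procedural assessments include any of the following". The list includes "subject request to end IP administration", a safety concern such as an adverse event, an administrative decision by the sponsor, and a decision by the investigator. Section 8.2 adds that the investigator or sponsor "can decide to withdraw a subject(s) from IP and/or other protocol-required therapies, protocol procedures, or the study as a whole at any time". Section 8.3.2, on leaving the study, lists a sponsor decision, withdrawal of consent, death and loss to follow-up. It lists no investigator decision.

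**Follow-up.** Section 6.2.2 says of a subject whom the investigator judges unable to tolerate IP "that subject will discontinue IP but will continue to return for all other study procedures and measurements until the EOS visit". Section 7.2 encourages every planned visit whatever the adherence to IP. Section 8.1 obliges the investigator to discuss continued assessments with a subject who declines IP. Section 12.4 makes the investigator responsible for "complying with the requirements for all assessments and data collection (including subjects not receiving protocol-required therapies" (bracket closed in the original).

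**Analysis.** SAP 10.5.1.1 states: "All LDL-C values observed will be used irrespective of whether a subject remained on IP". Nothing is imputed in the primary analysis, and SAP 9.3.2 names missing at random as the assumption. SAP 10.5.1.2 plans a sensitivity analysis that imputes a mean change of zero for those who stopped IP and have no endpoint value. It adds a second imputation from observed off-IP data if at least 25 evolocumab discontinuers have a week 24 value.

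**The concern.** The primary analysis depends on sampling people after they stop IP. Most of the protocol supports that sampling, but 8.3.1 attaches the reasons for ending IP to the ending of assessments as well. Two sites facing the same kind of IP stop could therefore act differently, each with a section to point to.

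Protocol Table 3 schedules fasting lipids after day 1 of the double-blind period only at weeks 12 and 24. A subject who stops evolocumab after week 12 and is not sampled again contributes one post-baseline value, taken on drug. Under missing at random, the model then in effect projects a week 24 value close to that of subjects still on drug. That is not the quantity SAP 10.5.1.1 sets out to use, and the error favours evolocumab. What is at stake is the size of the reported effect.

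**Working it through.** **1. The sections side by side, by reason for stopping IP**

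| IP stopped because | 6.2.2 | 8.3.1 | Other text |
|---|---|---|---|
| Investigator judges IP not tolerated | Visits continue to end of study | Safety concern or investigator decision can also end assessments | Direct conflict |
| Subject asks to stop IP | Silent | Can also end assessments | 8.1: continuation must be discussed; 7.2 encourages visits |
| Sponsor, or investigator for another reason | Silent | Can also end assessments | 7.2 encourages visits; 12.4 duty is in tension |

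Separately, 8.2 allows an investigator to withdraw a subject from the whole study, a route absent from 8.3.2.

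**2. The plan's power figure**

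Inputs (Protocol 10.2, SAP 3.2): 450 subjects at 2:1, effect 40 points, SD 20, two-sided alpha 0.05, dropout 10%. After dropout, 135 placebo and 270 evolocumab subjects remain.

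- Standard error = 20 × √(1/135 + 1/270) = 2.108.
- 40 / 2.108 = 18.97, far above 1.96. Power exceeds 99.99%, consistent with the stated figure of about 99%.
- Difference detectable with 99% power = (1.960 + 2.326) × 2.108 ≈ 9.0 points.

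**3. Possible overstatement**

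This model is an assumption of the review, not of the documents. A share d of the evolocumab arm stops IP and has no residual effect at week 24. A share r of those is still sampled. The unsampled are treated like the sampled. E is the on-drug effect.

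- Effect regardless of IP status = (1 − d) × E.
- Estimate obtained = (1 − d) × E / [(1 − d) + d × r].
- Overstatement when none are sampled (r = 0) = d × E.

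For E = 40, each 1% of the arm (3 of 300) gives 0.01 × 40 = 0.4 points. The documents give no IP discontinuation rate, so the planned 10% dropout stands in for d, with 5% to 20% as a range:

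| E | d | r | Effect regardless of IP | Estimate | Overstatement |
|---|---|---|---|---|---|
| 40 | 10% | 1 | 36.0 | 36.0 | 0 |
| 40 | 10% | 0.5 | 36.0 | 36.0/0.95 = 37.9 | 1.9 |
| 40 | 10% | 0 | 36.0 | 40.0 | 4.0 |
| 40 | 5% | 0 | 38.0 | 40.0 | 2.0 |
| 40 | 20% | 0 | 32.0 | 40.0 | 8.0 |
| 55.1 | 10% | 0 | 49.6 | 55.1 | 5.5 |
| 62.33 | 10% | 0 | 56.1 | 62.33 | 6.2 |

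The last two rows use the ends of the effect range quoted from the earlier phase 3 studies.

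**4. The second imputation**

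If 10% of 300, or 30 subjects, stop evolocumab, the threshold of 25 with week 24 data requires 25/30 = 83% to be sampled. Losing six leaves 24, and the analysis is not run.

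**The case against.** A reader might infer that off-IP week 24 LDL-C will be lost. The documents do not say so. Section 8.3.1 lists reasons and nowhere says that ending IP must end assessments. Sections 6.2.2, 7.2, 8.1 and 12.4 all favour continued sampling, and 7.2.3 asks for the week 24 procedures, if possible, when a subject leaves the study early. The text permits the loss; it does not require it.

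A reader might also infer that 12.4 flatly contradicts 8.3.1, or that 8.2 repeats the same reasons. Neither holds. The 12.4 duty runs only as far as the rest of the protocol stipulates, and it recognises subjects who "are unable or unwilling to continue the Schedule of Assessments (Table 3" (bracket closed in the original). Section 8.2 is a general power that names no reasons.

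The analysis plan also confronts this bias openly. The mean-zero imputation uses the same off-drug assumption as the working above, and both responder endpoints count a missing week 24 value as failure (SAP 6.3). This stands, but the imputation is a sensitivity analysis and leaves the primary estimate unchanged.

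The 7.2.3 safeguard is partial. It applies to leaving the study, and SAP Appendix A assigns lipids to week 24 only after day 126. An earlier sample maps to week 12, and a later one drawn soon after a dose could count as week 24 while still on drug.

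Finally, 10% dropout includes consent withdrawal, death and loss to follow-up, which no wording change recovers. A residual drug effect, or a week 12 value already taken off drug, would shrink the bias further. That objection to the size stands.

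**Conclusion.** The point holds as a drafting conflict with a possible effect on the primary estimate. Sections 8.3.1 and 6.2.2 give different answers for the same intolerant subject, and for other IP stops only softer language protects the week 24 sample. Missing off-IP values analysed as missing at random can overstate the effect.

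The size is unknown and starts at zero. It is about 0.4 points per 1% of the evolocumab arm that stops and is unsampled, given a 40-point effect, no residual effect off drug and filling with the on-drug mean. The 4 points at 10% is an upper bound under those assumptions, not an expected bias, because it charges all dropout to this wording.

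A reader might infer that the superiority conclusion is at risk. It is not: even 32 points, the lowest diluted value for E = 40 in the table, is far above the 9 points detectable with 99% power. The accuracy of the effect size is at issue, together with the possible loss of the second imputation in SAP 10.5.1.2. The change is worth making because it is nearly free.

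**What to change.** - In 8.3.1, delete *or procedural assessments*, so that the list governs IP only.
- In 6.2.2, extend the follow-up clause to every IP stop, whatever the reason, at least through the week 24 visit, unless the subject declines under 8.1 or leaves the study under 8.3.2.
- Reconcile 8.2 with 8.3.1 and 8.3.2 on whether an investigator decision can end assessments or study participation. This should not remove the ability to omit a specific procedure for safety.

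None of this alters a dose or a rule for stopping IP. The cost is protocol wording, since the visits and samples are already scheduled. The downside is a few more off-IP visits and possibly a slightly smaller estimated effect.

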8.3.2 Reasons for Removal From Study

Reasons for removal of a subject from the study are:

- decision by Amgen
- withdrawal of consent from study
- death
- lost to follow-up

Protocol Number: 20130286 Page 45 of 73

Product: Evolocumab Date: 30 January 2017

9. SAFETY DATA COLLECTION, RECORDING, AND REPORTING

9.1 **Definition of Safety Events**

9.1.1 **Disease-related Events**

Disease-related events are events (serious or non-serious) anticipated to occur in the study population due to the underlying disease. In this study, subjects are at risk for or are known to have cardiovascular disease. Therefore, disease-related events potentially include manifestations and complications of atherosclerotic vascular disease such as coronary artery disease, angina, MI, ischemic stroke, transient ischemic attack, carotid artery disease, peripheral vascular disease, and testing suggesting progression of atherosclerotic vascular disease. Such events do not meet the definition of an adverse event unless assessed to be more severe than expected for the subject's condition.

Disease-related events and/or disease related outcomes that do not qualify as adverse events or serious adverse events:

- An event which is part of the normal course of disease under study (eq. disease progression in oncology or hospitalization due to disease progression) is to be reported as a disease-related event.
- Death due to the disease under study is to be recorded on the Event CRF.

A disease-related event that would qualify as an adverse event or serious adverse event is an event based on the underlying disease that is worse than expected as assessed by the investigator for the subject's condition or an event for which the investigator believes there is a causal relationship between the investigational product(s)/study treatment/protocol required therapies and disease worsening. This must be reported as an adverse event or serious adverse event.

9.1.2 Adverse Events

An adverse event is defined as any untoward medical occurrence in a clinical trial subject. The event does not necessarily have a causal relationship with study treatment. The investigator is responsible for ensuring that any adverse events observed by the investigator or reported by the subject are recorded in the subject's medical record.

The definition of adverse events includes worsening of a pre-existing medical condition. Worsening indicates that the pre-existing medical condition or underlying disease (eg, diabetes, migraine headaches, gout) has increased in severity, frequency, and/or duration more than would be expected, and/or has an association with a significantly worse outcome than expected. A pre-existing condition that has not worsened more than anticipated (ie, more than usual fluctuation of disease) during the study or involves an

intervention such as elective cosmetic surgery or a medical procedure while on study, is not considered an adverse event.

The investigator's clinical judgment is used to determine whether a subject is to be removed from treatment due to an adverse event. In the event a subject, or subject's legally acceptable representative requests to withdraw from protocol-required therapies or the study due to an adverse event, refer to Section 8.1 for additional instructions on the procedures recommended for safe withdrawal from protocol-required therapies or the study.

The criteria for grade 4 in the Common Terminology Criteria for Adverse Events (CTCAE) grading scale differs from the regulatory criteria for serious adverse events. It is left to the Investigator's judgment to report these grade 4 abnormalities as serious adverse events.

9.1.2.1 **Worsening of HIV Disease**

HIV worsening will be captured as an adverse event. Because evolocumab is not expected to have any interaction with antiretroviral therapy or viral load or consequences of HIV infection, no specific actions with respect to study participation (including investigational product) are expected of the investigator. Should a subject's viral load change or HIV infection worsen, the investigator is expected to manage HIV infection or any other concomitant illnesses per his or her clinical judgment. Background lipid-lowering therapy is expected to be stable. However, in the case of HIV worsening, because of potential drug-drug interaction between statins and antiretroviral therapy, changing background lipid-lowering therapy is left to the judgment of the investigator.

9.1.3 **Adverse Device Effects**

An adverse device effect is any adverse event related to the use of a medical device. Adverse device effects include adverse events resulting from insufficient or inadequate instructions for use, adverse events resulting from any malfunction of the device, or adverse events resulting from use error or from intentional misuse of the device.

Protocol Number: 20130286 Page 47 of 73

Product: Evolocumab Date: 30 January 2017

9.1.4 **Serious Adverse Events**

A serious adverse event is defined as an adverse event that meets at least 1 of the following serious criteria (unless it meets the definition of a disease-related event provided in Section 9.1.1):

- fatal
- life threatening (places the subject at immediate risk of death)
- requires in-patient hospitalization or prolongation of existing hospitalization
- results in persistent or significant disability/incapacity
- congenital anomaly/birth defect
- other medically important serious event

A disease-related event is to be reported as a serious adverse event if:

- the subject's pre-existing condition becomes worse than what the investigator would consider typical for a patient with the same underlying condition, or
- if the investigator believes a causal relationship exists between the IMP/protocol-required therapies and the event,
- and the event meets at least 1 of the serious criteria above.

An adverse event would meet the criterion of "requires hospitalization," if the event necessitated an admission to a health care facility (eg, overnight stay).

If an investigator considers an event to be clinically important, but it does not meet any of the serious criteria, the event could be classified as a serious adverse event under the criterion of "other medically important serious event." Examples of such events could include allergic bronchospasm, convulsions, blood dyscrasias, DILI (see Appendix A for drug-induced liver injury reporting criteria), or events that necessitate an emergency room visit, outpatient surgery, or urgent intervention.

9.2 **Safety Event Reporting Procedures**

9.2.1 **Reporting Procedures for Disease-related Events**

The investigator is responsible for ensuring that all disease-related events observed by the investigator or reported by the subject that occur after randomization through EOS/safety follow-up visit, or 30 days after the last administration of IP, whichever is later, are reported on the Event CRF as disease related.

Disease-related events assessed by the investigator to be more severe than expected and/or related to the investigational medicinal product(s)/study treatment/protocol-required therapies and determined to be serious must be recorded on the event CRF as serious adverse events. Additionally, the

Protocol Number: 20130286

Date: 30 January 2017 Page 48 of 73

investigator is required to report a fatal disease-related event on the Event CRF as a disease-related event.

